11.5.7 Additional Exploratory Endpoints and Analyses - Open Label Stage

1. The following endpoints will only be evaluated in the Relivion®DP treatment group for the mITT analysis set:

- Change from Baseline to 16 weeks post Relivion®DP treatment initiation in HDRS-17 (Visit 6).

The change from baseline HDRS-17 score will be modeled with a repeated measures ANCOVA model. The change will be modeled as a function of visit (categorical) with baseline value entered as a covariate. LSmean changes in HDRS-17 scores will be estimated from the model per visit and for the difference between visits and will be presented with 95% confidence intervals as well as level of significance (testing the null hypothesis

LSmean=0). The change from baseline in HDRS-17 score at visit 6 will also be compared to the change at visit 4.

- **Proportion of HDRS-17 responder subjects to visit 6.** The percent of subjects achieving at least 50% reduction from baseline in HDRS-17 total score to each visit in the original active group will be summarized by a count and percentage and compared between the visits using a GEE model (repeated measures model for binary data) programmed in the SAS GENMOD Procedure which will account for the within subject correlation, baseline HDRS-17 score will be entered as a covariate.

- **Proportion of subjects achieving clinically substantial improvement in HDRS-17 scores to visit 6,** defined as the percent of subjects with reduction in HDRS-17 score of at least 7 points at 16 weeks post Relivion®DP treatment initiation.

The percent of subjects achieving clinically substantial improvement in HDRS-17 scores at each visit in the original active group will be summarized by a count and percentage and compared between the visits using a GEE model (repeated measures model for binary data) programmed in the SAS GENMOD Procedure which will account for the within subject correlation, baseline HDRS-17 score will be entered as a covariate.

- **Proportion of subjects achieving remission at visit 6** - defined as the percent of subjects with HDRS17 score≤7 at 16 weeks post Relivion®DP treatment initiation in the original active group. The percent of subjects achieving remission at each visit in the original active group will be summarized by a count and percentage and compared between the visits using a GEE model (repeated measures model for binary data) programmed in the SAS GENMOD Procedure which will account for the within subject correlation, baseline HDRS-17 score will be entered as a covariate.
- **HDRS-17 Category Shift from Visit 2 to Visit 6** – defined as the category change from baseline to week-16 post Relivion®DP treatment initiation in HDRS-17; Categories definition: 5: Very severe 26-52, 4: Severe 20-25, 3:

Moderate 14-19, 2: Mild 13-8 and 1: 0-7 Remission. The category shift will be tabulated and summarized by a count and percent.

- **Proportion of new responder subjects** - defined as the percent of subjects who did not have a remission (per HDRS-17) at visit 4, achieving at least 50% reduction from baseline (Visit 2) in HDRS-17 total score 16 weeks post Relivion®DP active treatment initiation (Visit 6). A count and percentage with two-sided exact 95% confidence interval will be presented.
- **Proportion of new subjects achieving remission** - defined as the percent of subjects who did not have a remission (per HDRS-17) at visit 4, achieving a HDRS-17 total score \leq 7 points 16 weeks post Relivion®DP active treatment initiation (Visit 6). A count and percentage with two-sided exact 95% confidence interval will be presented.
- **Change from baseline to 16 weeks (Visit 6) post Relivion®DP treatment initiation in the Clinical Global Impression Severity scale (CGI-S) score.** The change from baseline CGI-S score will be modeled with a repeated measures ANCOVA model. The change will be modeled as a function of visit (categorical) with baseline value entered as a covariate. LSmean CGI-S changes from baseline will be estimated from the model per visit and for the difference between visits and will be presented with 95% confidence intervals as well as level of significance (testing the null hypothesis LSmean=0). The change at visit 6 will also be compared to the change at visit 4.
- **Clinical Global Impression Improvement (CGI-I) score over time to Visit 6.** The CGI-I score (from visit 3) will be modeled with a repeated measures ANCOVA model. The score will be modeled as a function of visit (categorical). LSmean CGI-I scores will be estimated from the model per visit and for the difference between visits and will be presented with 95% confidence intervals as well as level of significance (testing the null hypothesis LSmean=0). The CGI-I score at visit 6 will be compared to the score at visit 4.

- **Change from baseline to week-16 (visit 6) post Relivion®DP treatment initiation in the total score of the Quick Inventory of Depressive Symptomatology (self-rated) (QIDS-SR-16).** The change from baseline QIDS-SR-16 score will be modeled with a repeated measures ANCOVA model. The change will be modeled as a function of visit (categorical) with baseline value entered as a covariate. LSmean QIDS-SR-16 changes from baseline will be estimated from the model per visit and for the difference between visits and will be presented with 95% confidence intervals as well as level of significance (testing the null hypothesis LSmean=0). The change at visit 6 will also be compared to the change at visit 4.
- **Change from baseline Q-LES-Q score at Visit 6** – measured as the difference between the baseline and visit 6 Q-LES-Q percentage of maximum total scores. The change from baseline Q-LES-Q score will be modeled with a repeated measures ANCOVA model. The change will be modeled as a function of visit (categorical) with baseline value entered as a covariate. LSmean Q-LES-Q changes from baseline will be estimated from the model per visit and for the difference between visits and will be presented with 95% confidence intervals as well as level of significance (testing the null hypothesis LSmean=0). The change at visit 6 will also be compared to the change at visit 4.

2. The following endpoints will be analyzed on all subjects that completed visit 6 grouped together regardless of prior double-blind treatment:

- **SIQ (Satisfaction Questionnaire) Question #2:** Proportion of subjects rating the subjects convenience (score of 1, 2 and 3) to undergo a depression treatment that required a daily treatment (5-7 days a week) or maintenance treatment, defined as Very convenient, Somewhat convenient or Neutral, neither convenient nor inconvenient using a simple Likert-type scale whereas 1 = Very convenient, 2 = Somewhat convenient, 3 = Neutral, neither convenient nor inconvenient, 4 = Somewhat inconvenient, 5 = Very inconvenient, will be summarized by a count and

percentage and will be presented with two-sided exact 95% confidence interval.

- **SIQ (Satisfaction Questionnaire) Question #3:** Proportion of subjects rating the subjects convenience (score of 1, 2 and 3) to undergo a home based self-operated depression treatment, defined as Very convenient, Somewhat convenient or Neutral, neither convenient nor inconvenient using a simple Likert-type scale whereas 1 = Very convenient, 2 = Somewhat convenient, 3 = Neutral, neither convenient nor inconvenient, 4 = Somewhat inconvenient, 5 = Very inconvenient, will be summarized by a count and percentage and will be presented with two-sided exact 95% confidence interval.
- **SIQ (Satisfaction Questionnaire) Question #6:** Proportion of subjects rating the subjects ease (score of 1, 2 and 3) to administer the Relivion®DP treatment, defined as Very easy, easy , Neutral, using a simple Likert-type scale whereas 1 = Very easy, 2 = Easy, 3 = Neutral, 4 = Challenging, 5 = Difficult, will be summarized by a count and percentage and will be presented with two-sided exact 95% confidence interval.
- **SIQ (Satisfaction Questionnaire) Question #11:** Proportion of subjects satisfied from the study device effect on their depression status (score of 1 and 2), defined as Very satisfied and Satisfied, using a simple Likert-type scale whereas 1 = Very satisfied, 2 = Satisfied, 3 = Unsure, 4 = Dissatisfied, 5 = Very dissatisfied, will be summarized by a count and percentage and will be presented with two-sided exact 95% confidence interval.

3. The following endpoint will be evaluated in all subjects who did not achieve remission in the double-blind phase for the mITT analysis set regardless of prior double-blind treatment:

- **Change from visit 4 to 16 weeks post Relivion®DP treatment initiation in HDRS-17 (Visit 6).** The change from visit 4 HDRS-17 score will be modeled with an ANCOVA model with baseline value entered as a covariate. LSmean changes in HDRS-17 scores will be estimated from the model and will be

presented with 95% confidence intervals as well as level of significance (testing the null hypothesis LSmean=0).

STATISTICAL

Final Audit Report

2024-05-29

Created:	2024-05-29
By:	[name] ([contact])
Status:	Signed
Transaction ID:	CBJCHBCAABAACkzPbHHLGM-xTDT9BogVTL12s5EmyqHM

"STATISTICAL" History

-  Document created by [name] ([contact])
2024-05-29 - 11:16:33 AM GMT
-  Document emailed to [name] ([contact]) for signature
2024-05-29 - 11:16:39 AM GMT
-  Document emailed to [name] ([contact]) for signature
2024-05-29 - 11:16:39 AM GMT
-  Document emailed to [name] ([contact]) for signature
2024-05-29 - 11:16:39 AM GMT
-  Document emailed to [name] ([contact]) for signature
2024-05-29 - 11:16:39 AM GMT
-  Email viewed by [name] ([contact])
2024-05-29 - 11:17:44 AM GMT
-  Document e-signed by [name] ([contact])
Signature Date: 2024-05-29 - 11:18:49 AM GMT - Time Source: server
-  Email viewed by [name] ([contact])
2024-05-29 - 11:29:52 AM GMT
-  Document e-signed by [name] ([contact])
Signature Date: 2024-05-29 - 11:31:46 AM GMT - Time Source: server
-  Email viewed by [name] ([contact])
2024-05-29 - 12:16:36 PM GMT
-  Document e-signed by [name] ([contact])
Signature Date: 2024-05-29 - 12:21:54 PM GMT - Time Source: server

Adobe Acrobat Sign

 Email viewed by [name] ([contact])

2024-05-29 - 3:31:37 PM GMT

 Document e-signed by [name] ([contact])

Signature Date: 2024-05-29 - 3:32:12 PM GMT - Time Source: server

 Agreement completed.

2024-05-29 - 3:32:12 PM GMT

Adobe Acrobat Sign

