We use conservative estimates of a 3.3-point difference with a standard deviation of 6 points. Calculations show that a sample size of 53 subjects per group (total 106) would provide 80% power at a 5% level of significance (two-sided) to detect the difference between treatment and sham groups.

Given our preliminary results, together with other companies clinically relevant data, we hypothesize that our statistical assumptions are aligned with competitive treatments for MDD.

The company anticipates that after randomization, but before the endpoint can be observed, up to 15% of the subjects will drop out from the study irrespective of study arm and success of treatment; thus, an adjustment for this drop-out rate is made and a sample size of 124 is required at the point of randomization.

We shall randomize an additional up to 36 subjects (30+15% dropout) in the age range 18-21 to assess efficacy in this age range as well.

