11.5 Endpoints Analyses

11.5.1 Primary Efficacy Endpoint Analyses

The primary efficacy endpoint is the change from baseline to 8 weeks post treatment initiation in HDRS-17 score.

The change in HDRS-17 from baseline to 8 weeks post treatment initiation will be compared between the treatment groups using a repeated measures analysis of covariance (ANCOVA, SAS® MIXED procedure). The model will include the following fixed effects: treatment group, visit, treatment group by visit interaction

with Baseline HDRS-17, and center entered as covariates. If covariates are identified in the prognostic factor analysis, they may be added to the model as well. Baseline HDRS-17 scores will be entered as a continuous variable so that the potential for co-linearity problems will be minimized. The treatment group by center interaction will be evaluated as well, but not as part of the principal statistical evaluation.

The unstructured covariance matrix structure will be used. If the model does not converge, then either the compound symmetry or autoregressive (whichever model has the lower AIC statistic) covariance matrix structure will be used instead. At this time point (up to 8 weeks) we do not expect a high proportion of dropouts, as a placebo effect of the sham treatment is expected and was taken into consideration in the design of the study. Thus, any missing data at 8 weeks post treatment initiation can be considered missing at random. Therefore, since repeated measures ANOVA is also an imputation method, for this evaluation no other method of imputation of missing data is considered beyond the model estimates. Nevertheless, should the missing at random assumption prove to be incorrect, a sensitivity analysis using other methods for data imputation mentioned in Section 7 may be performed.

Mock SAS code for the analysis:

```
Proc Mixed data=HDRS17;
  class visit group center subjectid;
  model change_HDRS17 = baseline_HDRS17 visit group visit*group;
  repeated / type=un subject=subjectid;
  lsmeans group*visit / pdiff cl;
  random center;
run;
```

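### The per-visit 95% intervals for mean change in the single-arm open-label models treat the sample mean baseline as fixed and are therefore somewhat too narrow

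*SAP*

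**What the plan says.** SAP 11.5.7 (open-label stage) limits item 1 to one arm: "The following endpoints will only be evaluated in the Relivion®DP treatment group for the mITT analysis set". For HDRS-17, "The change will be modeled as a function of visit (categorical) with baseline value entered as a covariate". It continues: "LSmean changes in HDRS-17 scores will be estimated from the model per visit and for the difference between visits". Each estimate is given with a 95% interval and a test that the LSmean is zero. The same model is set for CGI-S ("LSmean CGI-S changes from baseline will be estimated from the model per visit"), for QIDS-SR-16 and for Q-LES-Q ("LSmean Q-LES-Q changes from baseline will be estimated from the model per visit"). The CGI-I model has no baseline covariate.

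Item 3 covers subjects from both arms who were not in remission at the end of the double-blind phase: "The change from visit 4 HDRS-17 score will be modeled with an ANCOVA model with baseline value entered as a covariate". It does not say whether baseline there means Visit 2 or Visit 4.

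The SAP does not state the baseline value at which the open-label LSmeans are taken. The only mock code belongs to the primary model in SAP 11.5.1. It reads "lsmeans group*visit / pdiff cl" and sets no reference value. Nothing says that the intervals are meant to be conditional on the observed baselines.

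**The concern.** SAP 11.4 justifies ANCOVA by chance imbalance between randomised groups and by the precision of the treatment effect. Neither reason carries over to the mean of a single arm. In a difference between arms or between visits, the mean baseline at which the LSmeans are taken cancels. In a single-arm mean it stays in the estimate, but the model's standard error treats it as a known constant.

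The resulting interval is right for a group whose mean baseline is fixed at the observed value. The endpoint, however, is simply named as change from baseline to week 16, and a reader will take the interval as one for the mean change under treatment. On that reading, the per-visit intervals and tests claim more precision than the data hold, and always in that direction.

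**Working it through.** **Inputs.** Protocol 12.4: "We use conservative estimates of a 3.3-point difference with a standard deviation of 6 points", with 53 evaluable subjects per arm, 80% power and a two-sided 5% level. The baseline SD and r are not in the documents and are assumed below. LSmeans are assumed to be taken at the sample mean baseline.

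**The plan's own figure.** The normal approximation gives n = 2 x (1.960 + 0.842)^2 x 36 / 3.3^2 = 51.9, so 52 per arm. The noncentral t gives power of 79.3% at 52 and 80.1% at 53, so the stated 53 is reproduced. It serves here only to set n and the SD.

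**Algebra, complete data.**
- The LSmean at the sample mean baseline equals the raw mean change.
- Its true standard error is SD/sqrt(n) = 6/sqrt(53) = 0.824.
- Let b be the slope shared across visits, b_v the visit's own slope and s the baseline SD. The model's variance is [SD^2 (1 - r^2) + (b - b_v)^2 s^2]/n.
- If b = b_v, the model's standard error is 0.824 x sqrt(1 - r^2). If the slopes differ, the narrowing is smaller. The factor sqrt(1 - r^2) is therefore the maximum narrowing.
- Real coverage is about 2 Phi(1.96 sqrt(1 - r^2)) - 1.

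| abs(r) | Factor | Half-width, points | Too narrow by | Real coverage |
|---|---|---|---|---|
| 0 | 1.000 | 1.65 | 0% | 95.0% |
| 0.2 | 0.980 | 1.62 | 2% | 94.5% |
| 0.3 | 0.954 | 1.58 | 5% | 93.9% |
| 0.4 | 0.917 | 1.52 | 8% | 92.8% |
| 0.5 | 0.866 | 1.43 | 13% | 91.0% |

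**Plausible r (assumed).** Take a follow-up SD of 6, a baseline SD s of 3 to 5 and a baseline/follow-up correlation rho of 0.2 to 0.5. Then r = (6 rho - s)/sqrt(s^2 + 36 - 12 rho s).
- s = 3, rho = 0.5: r = 0, no narrowing.
- s = 4, rho = 0.3: r = -2.2/6.13 = -0.36, factor 0.933, coverage 93.3%.
- s = 5, rho = 0.2: r = -3.8/7.0 = -0.54, factor 0.840, coverage 90.0%.

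The feasibility results in Protocol 12.4 do not settle r. The interval half-widths of 2.15 and 2.17 with 23 completers imply an SD of about 5.0, close to the pooled value of the two stated SDs (4.95).

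**Simulation of the planned model.** Four visits, one shared slope, unstructured covariance, n = 53, SD of change 6, baseline SD 4, complete data.
- Slope of change on baseline -0.55 (r = -0.55 x 4/6 = -0.37), 3,000 runs: the LSmean equalled the raw mean in every run. The true SE was 0.826 and the model SE 0.766 (7% too small), with coverage of 93.4%. Without the covariate the model SE was 0.820 and coverage 95.2%.
- Slope -0.75 (r = -0.50), 800 runs: true SE 0.838, model SE 0.716, coverage 90.9%. A separate simulation gave 92% at this r.
- Visit 6 minus Visit 4 (slope -0.55): coverage 95.6% with the covariate and 95.5% without.

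**Missing Visits 5 and 6.** Slope -0.55, with dropout depending on baseline (about 23% on average), 1,200 runs.

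| Model | Bias at Visit 6 | Model SE / true SE |
|---|---|---|
| No covariate | 0.25 | 0.915 / 0.938 |
| Covariate, LSmean at the record-weighted mean | 0.19 | 0.873 / 0.934 |
| Covariate, LSmean at the mean of all subjects | 0.00 | 0.876 / 0.933 |

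The covariate reduces bias here, and removes it at the all-subject mean. The model SE is still about 6% too small (0.876/0.933 = 0.94).

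**The case against.** The strongest reply is that LSmeans at the observed mean covariate are ordinary model output, valid conditional on the observed baselines, so this is a choice of target rather than an error. That would stand if the SAP said so. It names the endpoint simply as change from baseline and states no conditional target.

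A reader might also infer that the covariate does nothing and can be removed. That is exact only with complete data. Protocol 8.2 makes open-label entry the subject's choice, so Visits 5 and 6 will be missing for some, and the simulation shows that baseline information then matters.

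A reader might put the shortfall as high as 25%, with 86% coverage. That needs r = -4/6 = -0.67, meaning a baseline SD of 4 and no relation at all between baseline and later HDRS-17. Nothing in the documents supports so extreme a case. A slope of the later score on baseline close to 1 would give almost no narrowing.

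It is also true that the consequence is small. At |r| = 0.4 the half-width is 1.52 instead of 1.65 points. If the change resembled the feasibility mean of -8.4, it would lie about 10 standard errors from zero (8.4/0.824). Persistence of effect is also judged by the Visit 6 versus Visit 4 contrasts and by the response and remission rates, where this problem does not arise.

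**Conclusion.** The point holds as a minor one. In item 1, the per-visit intervals and zero-change tests for HDRS-17, CGI-S, QIDS-SR-16 and Q-LES-Q overstate precision for the active arm's mean change. With |r| up to about 0.5, an SD of change of 6 and n = 53, they are about 0 to 15% too narrow, and coverage is 95% down to 90-91%. This rests on assumed values of r and the baseline SD and on LSmeans taken at the sample mean baseline. The 6-point SD applies to HDRS-17; for the other scales only the factor carries over.

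Item 3 has the same structure, but the effect there is not quantified. It would be wrong to infer that the open-label results as a whole are invalid or that the randomised comparison is touched. The between-visit contrasts, CGI-I and the primary treatment difference are unaffected, and the zero-change conclusions are unlikely to alter.

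**What to change.** For item 1 of SAP 11.5.7, model the score itself at every visit where it is measured, with Visit 2 as one of the repeated responses, unstructured covariance and no baseline covariate. Report each visit minus Visit 2. This gives the unconditional standard error and keeps the baseline information of subjects with missing later visits, under the missing-at-random assumption that the SAP already makes.

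Alternatively, keep the covariate, take the LSmean at the mean baseline of all mITT active subjects, state this, and add slope^2 x s_baseline^2 / n to its variance. The two approaches agree when one slope fits all visits. If it does not, a baseline-by-visit term is needed.

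For item 3, report the mean Visit 6 minus Visit 4 change with its unconditional standard error.

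The cost is a change of SAP wording, a recoded exploratory model and slightly wider intervals. No data collection changes.

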(visit 3) and at  $8\pm 1$  weeks post visit 2 (visit 4). During visits 3 and 4 subject's depression symptoms will be assessed by the site team qualified raters using the study questionnaires and the subject self-reported questionnaire. Study visit 4 will be the end of the double-blind phase and the beginning of the open label extension period. At this visit, subject's compliance with the treatment regimen during the DB phase will be assessed. Subjects who would not fulfill the minimum stimulation requirements during the DB phase (non-compliant subjects) will complete their participation in the study. DB phase treatment regimen compliant subjects will be offered to participate in a  $8\pm 1$  weeks open-label period with an active device. Subjects who choose to continue to the open label phase will be trained as per their recommended treatment regimen (see Figure 5) by the study central trainer in an on-site or remote fashion. (regardless their prior DB treatment assignment) and will follow this treatment regimen for the next 4-8±1 weeks. Subjects will return for follow up visits (on-site or remote) at  $4\pm 1$  weeks post visit 4 (visit 5) and at  $8\pm 1$  weeks post visit 4 (visit 6). During visits 5 and 6 subject's depression symptoms will be assessed by study team qualified raters and the PRO (electronic or hard copy) using the study questionnaires. At study visit 5 the subjects response to treatment, according to HDRS, will be re-evaluated and treatment regimen may be amended accordingly (see Figure 5), re-training will be performed by the central trainer, if required. Study visit 6 will be the end of study visit during which the device will be returned, final data will be collected, and the subjects will be exited from the study.

Subjects found ineligible by the procedures required at screening will be marked as 'screen failure' on the screening & enrollment log and will not take part in the study. Screen failure subjects will not be included in the intention-to-treat analysis, nor will they be counted as part of the target subject sample number.

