### **9.1.5. Visit 4 – end of the DB phase (Day 56±7)**

Written below are the assessments to be completed at Visit 4 (either on site or remotely):

[figure not shown]
- Depression symptoms questionnaires:
  - By site qualified rater: HDRS21 (HDRS17- removing 4 last questions from the HDRS21), MDRS, CGI-S & CGI-I
  - By subject: QIDS-SR-16, Q-LES-Q. Subject self-reported questionnaire may be filled in electronically (ePRO) or by hard copy.
- Suicidal intent assessment by the investigator team (C-SSRS)
- Change in concomitant medications, if any.
- Significant change in health status, if any.
- Adverse events will be documented.
  - The characteristics of each subject study treatments regimen will be indicated on the subject binder.
  - At the end of the double-blind treatment phase treatment compliance would be verified as follows:
    - A stimulation session marked as “Pass” if a minimal average intensity of 25 on the Relivion®DP app (i.e= Minimal average stimulation of 2.57mA Trigeminal, and 6.92mA Occipital of the active stimulation), was delivered.
    - The first treatment week (Ramp Up) will not be counted for treatment compliance.
    - Expected treatment time for total DB phase: A total of 2400 minutes of “pass” treatment time (calculated as a scenario of 80 min per day, 5 days a week for 6 weeks).
    - Minimal patient compliance for the DB treatment period will be regarded as 70% compliance to the above cumulative “pass” stimulation time recommendation.
- DB treatment regimen compliant subjects will be offered to continue to the open label extension phase for additional 8±1 weeks.
- Treatment regimen non-compliant subjects will exit the study and return the device and iPhone, if provided. For these subjects this study visit would be the “end of study visit”.

- Once the OL treatment regimen allocation will be decided, the central trainer will contact the subject (on site or remote) to perform the device conversion to the open label mode (i.e. conversion of all devices to active mode), train the subjects on the assigned treatment regimen and re-train on the device use, if required.
- OL treatment regimens would include:
  - Maintenance treatment (for remitters): 40±10 minutes 3-4 times a week (intensity level up to 50)
  - Daily treatment (for responders): 5-7 days a week (intensity level up to 50) 60±20 minutes per day (preferably in two equal sessions of 30±10 minutes each).

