7. MISSING DATA HANDLING & SENSITIVITY ANALYSES

The study outcomes will not be evaluated for patients who drop out prior to randomization. The primary endpoint will be analyzed using a repeated measures ANCOVA model which can handle data missing at random and we do not expect a high proportion of dropouts until the primary endpoint is measured. Therefore, for this evaluation no imputation of missing data is considered beyond the model estimates. Additionally, imputation of data such as by LOCF may harm linearity in such models, therefore, for this evaluation no imputation of missing data is considered beyond the model estimates.

Nevertheless, a sensitivity analysis based upon last observed values (LOV) may be performed. The Last Observed Value (LOV) is defined as the last available post baseline visit data up to and including the last treatment visit or termination visit. For categorical variables (such as response and remission rates at week 8) the LOCF concept will be applied. Baseline characteristics of patients who drop out will be evaluated by study group to evaluate the potential reason for differential drop out if needed.

The primary endpoint analysis, using the same methods described, will also be performed on the PP and ITT analysis sets as sensitivity analyses.

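### The open-label response, 7-point improvement and remission rates are compared across visits by an unweighted GEE, with no stated rule for active mITT subjects who decline or leave open label

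*SAP*

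**What the plan says.** SAP 11.5.7 opens its first block with the analysis set: "The following endpoints will only be evaluated in the Relivion®DP treatment group for the mITT analysis set". Response and 7-point improvement in the original active group "will be summarized by a count and percentage and compared between the visits using a GEE model", run in the GENMOD procedure with baseline HDRS-17 as the covariate. Remission is handled the same way: "The percent of subjects achieving remission at each visit in the original active group will be summarized by a count and percentage" and then compared between visits by GEE. The section says that the model accounts for within-subject correlation. It gives no working correlation, weights, denominator for Visits 5 and 6, or sensitivity analysis for open-label attrition.

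Protocol 8.2 offers open label to subjects who complied with the double-blind regimen, and entry is a choice: "Subjects who choose to continue to the open label phase will be trained as per their recommended treatment regimen". Protocol 9.1.5 adds a compulsory exit for the others: "Treatment regimen non-compliant subjects will exit the study and return the device and iPhone, if provided".

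SAP 7 has one missing-data rule for binary outcomes: "For categorical variables (such as response and remission rates at week 8) the LOCF concept will be applied". Week 8 is given as an example and week 16 is not mentioned. The missing-at-random argument in SAP 11.5.1 is made for the primary model up to 8 weeks.

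**The concern.** A subject can be in the active mITT at Visit 4, decline open label, and have no Visit 5 or 6 record. An unweighted GEE on available records is generally safe only if leaving is unrelated to outcome, given the covariates in the model. Baseline HDRS-17 does not carry what happened between baseline and Visit 4, and Visit 4 outcome is an obvious influence on whether a subject continues. The raw count and percentage at each visit have the same weakness, and no working correlation repairs them.

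The other possible reading has its own difficulty. If carry-forward reaches open-label visits, a subject who declined open label is scored at Visit 6 on Visit 4 status, without having had open-label treatment.

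At stake is the description of how response and remission hold up to week 16, in a trial that SAP 1 says is meant to support marketing applications. Part of any change between Visits 4 and 6 could reflect who stayed.

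**Working it through.** **Inputs.** The plan states no figure for this analysis, so there is none to reproduce.
- Visit 4 response rate p = 8/23 = 0.348. This is the 6-week feasibility result in Protocol 7.6.2, used here as an assumption for week 8.
- n = 53, the evaluable number per group in Protocol 12.4. That number itself reproduces: 2(1.960 + 0.842)²/(3.3/6)² = 51.9 by the normal formula, and 52.9 by the t-test, so 53.
- lN and lR, the shares of Visit 4 non-responders and responders with no Visit 6 record. These are assumptions; the documents give no open-label attrition figure.
- c, the share of subjects whose Visit 6 status is redrawn at rate p. The true rate is therefore p at both visits and the true change is zero. Also an assumption.

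**Formulas when leaving depends on Visit 4 status.** Let L = p·lR + (1-p)·lN be the share leaving, and let q be the share of Visit 4 responders among those who stay:

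q = p(1-lR) / [p(1-lR) + (1-p)(1-lN)]

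The spurious Visit 4 to Visit 6 change is then:
- available data, independence GEE: (1-c)(q-p)
- carry-forward: -c·p(1-p)(lN-lR)
- subjects with both visits: -c(q-p)
- full denominator, missing counted as non-response: (1-L)[(1-c)q + cp] - p
- GEE weighted by a correct model for leaving given Visit 4 status: 0 in large samples

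**One case in full (lN = 0.40, lR = 0.05).** q = 0.330/(0.330 + 0.391) = 0.458. If nobody changes status (c = 0), available data give 45.8% against 34.8%, or +11.0 points, and carry-forward gives 0. With c = 0.4, available data give 0.6 × 11.0 = +6.6; carry-forward gives -0.4 × 0.227 × 0.35 = -3.2; both-visits gives -0.4 × 11.0 = -4.4; missing as non-response gives 0.722 × 0.414 - 0.348 = -4.9.

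**Spurious change in percentage points**

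| lN / lR | Available, c = 0 | Available, c = 0.4 | Carry-forward, c = 0.4 | Both visits, c = 0.4 | Missing = non-response, c = 0.4 |
|---|---|---|---|---|---|
| 10% / 5% | +1.2 | +0.7 | -0.5 | -0.5 | -2.2 |
| 20% / 5% | +4.0 | +2.4 | -1.4 | -1.6 | -3.1 |
| 30% / 5% | +7.2 | +4.3 | -2.3 | -2.9 | -4.0 |
| 40% / 5% | +11.0 | +6.6 | -3.2 | -4.4 | -4.9 |
| 5% / 30% | -6.6 | -3.9 | +2.3 | +2.6 | -8.2 |
| 20% / 20% | 0.0 | 0.0 | 0.0 | 0.0 | -7.0 |

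Carry-forward gives 0.0 in every row when c = 0.

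**Working correlation.** Solving the two-visit exchangeable GEE for the same mechanism, with 20 to 40% of non-responders and 5% of responders leaving and c from 0.3 to 0.6, gives about 0 to -1 point. If leaving depends instead on the unobserved Visit 6 status, the exchangeable GEE gives about +2 to +9 points, and weighting on Visit 4 data would not remove that bias.

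**Scale.** The standard error of the change is about √[2c·p(1-p)/n], ignoring attrition. At n = 53 that is 5.1 points for c = 0.3, 5.9 for c = 0.4 and 7.2 for c = 0.6.

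**The case against.** A reader might infer that the SAP analyses only those who remain and will therefore show a gain. The documents do not say that. The stated population is the active mITT. The carry-forward rule introduces week-8 rates only as examples, so it can be read as keeping leavers in the denominator. Nor is it right that both readings must give a wrong rate: if no individual changes status, carry-forward is exact.

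The direction is also open. Non-responders have reasons to stay: every compliant subject is offered an active device whatever the earlier assignment (Protocol 8.2), and non-responders move to a different regimen (Protocol 6.3.2). If responders leave more often, the available-data contrast moves down. The upward shift further needs a working correlation that the SAP does not specify.

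The compulsory exit of non-compliant subjects adds nothing. Protocol 12.7.2 requires the minimal stimulation time, so those subjects are outside the mITT at every visit. The SAP's own mITT text was not available for this review.

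Finally, these endpoints are labelled exploratory, have no control arm, and lie outside the testing hierarchy of SAP 9.2. No passage says that they will support a claim of sustained benefit. SAP 11.5.7 also has a repeated-measures model for HDRS-17 change, and SAP 11.3 reports completion by stage and time to withdrawal.

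All of this stands, and it limits direction, size and importance. It does not supply the missing rule. The disposition tables show who left but do not correct the rates.

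**Conclusion.** The point holds as a gap in method with limited consequence. The SAP compares binary outcomes across visits with an unweighted GEE, entry to the later visits is voluntary, and treatment of the absent records is undefined.

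Under available data with independence, leaving related to Visit 4 status alone shifts the contrast by +1.2 to +11.0 points (10 to 40% of non-responders and 5% of responders leaving, no status change), or by -6.6 points in the reverse case. With 40% of subjects redrawn, the ranges are +0.7 to +6.6 and -3.9. Carry-forward then errs by -0.5 to -3.2, or +2.3. The larger shifts are about the size of one standard error at n = 53.

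These figures rest on an assumed Visit 4 rate, assumed leaving and redrawing, and a two-visit simplification without the baseline covariate. They show what the unspecified choices can do; they do not predict this trial's result. Priority is low.

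**What to change.** In SAP 11.5.7, for the three binary endpoints:
- Make the visit comparison with a weighted GEE, with weights from a model for remaining under observation given Visit 4 HDRS-17, Visit 4 response and baseline. Alternatively, multiply impute HDRS-17 from the repeated-measures model and derive the binary outcomes from it. Name the working correlation.
- State that the SAP 7 carry-forward rule is not used for open-label visits.
- Report the number observed at each visit beside every percentage.
- Add two labelled sensitivity analyses: the Visit 6 rate on the full active mITT denominator with missing counted as non-response, described as a conservative bound; and Visit 4 against Visit 6 in subjects with both. Neither should be the main analysis, because the table shows that both are biased under the same mechanism.

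Weighting and imputation still assume that leaving depends on recorded data, and the text should say so. The cost is a short SAP revision, minor programming, and possibly less favourable Visit 6 rates.
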